5.1. Inclusion Criteria

Participants are eligible to be included in the study only if all of the following criteria apply:

Age and Sex:

1. Participants aged 18 years to 70 inclusive (or the minimum age of consent in accordance with local regulations) at screening.
 - Refer to [Appendix 4](#) for reproductive criteria for male ([Section 10.4.1](#)) and female ([Section 10.4.2](#)) participants.

Disease Characteristics:

2. Previous diagnosis of CeD, based on documentation in the source data:
 - Positive celiac serology (eg, tissue transglutaminase IgA antibody and/or deamidated DGP IgG)

AND

 - Intestinal histology consistent with \geq Marsh Type 2 ([Section 10.11](#)) or with evidence of villous atrophy.
3. Have HLA-DQ2.5 genotype (HLA-DQA1*05 and HLA-DQB1*02 (homozygotes or heterozygotes)).
4. Negative or weak positive for transglutaminase IgA AND negative or weak positive for DGP-IgA/IgG during screening.
 - For tTG, a result of ≤ 10 U/mL will be considered negative or weak positive.
 - For DGP, a result of < 30 U/mL will be considered negative or weak positive.
5. **Part B ONLY (prior to randomization):** Demonstrates a symptomatic response following a 1-day oral GC performed during Run-in, defined as having at least 1 moderate to severe GI symptom (either diarrhea, abdominal pain, bloating, or nausea) the day of the GC.
 - Refer to [Section 8.2.1.1](#) for symptomatic response criteria.

Other Inclusion Criteria:

6. Have followed a gluten-free diet for ≥ 12 months immediately prior to study entry (self-reported).
7. Capable of understanding the ICD, complying with protocol requirements, and has signed the ICD.

5.2. Exclusion Criteria

Participants are excluded from the study if any of the following criteria apply:

Medical Conditions:

1. Refractory CeD, defined as severe persistent or recurrent malabsorptive signs or symptoms with substantial villous atrophy (ex. documented Marsh score 3c in source data) despite strict adherence to a GFD for at least 12 months in the absence of other disorders.
2. Selective IgA deficiency.
3. Positive for HLA-DQ8 (*DQA1*03*, *DQB1*0302*).
4. Known wheat allergy.
5. Known history of severe hypersensitivity reactions or anaphylaxis to gluten.
6. Previous oral GC within 12 months.
7. History of dermatitis herpetiformis.
8. Active gastrointestinal disease (eg, inflammatory bowel disease, any forms of colitis, uncontrolled IBS, peptic ulcer disease, eosinophilic esophagitis, and active GI infections).
9. Diagnosis of Type-I diabetes.
10. Clinical signs and symptoms consistent with COVID-19 or confirmed infection by appropriate laboratory test within the 2 weeks prior to screening or dosing.
 - *Note:* participants who experienced symptoms consistent with COVID-19 or confirmed infection during the screening period may be rescreened after 4 weeks.
11. Prior severe course of COVID-19 requiring extracorporeal membrane oxygenation or mechanical ventilation within the last 12 months.

12. Other uncontrolled or significant medical (including active infections) or psychiatric condition including recent (within the past year) or active suicidal ideation/behavior or laboratory abnormality that may increase the risk of study participation or, in the investigator's judgment, make the participant inappropriate for the study.

Prior/Concomitant Therapy:

13. Previous treatment with tolerance-inducing therapies for CeD.
14. Current use of any prohibited concomitant medication(s) or participants unwilling/unable to use a permitted concomitant medication(s). Refer to [Section 6.9](#) Prior and Concomitant Therapy.

Prior/Concurrent Clinical Study Experience:

15. Previous administration with an investigational product (drug or vaccine) within 30 days (or as determined by the local requirement) or 5 half-lives preceding the first dose of study intervention used in this study (whichever is longer).

Diagnostic Assessments:

16. Renal impairment as defined by an eGFR in adults of $<60 \text{ mL}/\text{min}/1.73\text{m}^2$. Based upon participant age at screening, eGFR is calculated using the recommended formulas in [Section 10.7.2](#) to determine eligibility and to provide a baseline to quantify any subsequent kidney safety events.

17. Hepatic dysfunction defined as:

- Total bilirubin $\geq 1.5 \times \text{ULN}$ (except for Gilbert's syndrome)
- AST $\geq 1.5 \times \text{ULN}$
- ALT $\geq 1.5 \times \text{ULN}$
- Alkaline phosphatase $> 1.5 \times \text{ULN}$

18. Hematologic abnormalities defined as:

- ANC $\leq 1000 \text{ mm}^3$
- Platelets $\leq 100 \times 10^9/\text{L}$
- Hemoglobin $\leq 10 \text{ g}/\text{dL}$
- WBC outside the normal range and assessed as clinically significant by the investigator.

19. Positive for HIV, hepatitis B, and/or hepatitis C.

- For Hepatitis B, all participants will undergo testing for HBsAg and HBcAb during screening. Participants who are HBsAg positive are not eligible for the study. Participants who are HBsAg negative and HBcAb positive will be reflex tested for HBsAb and HBV DNA. If HBsAb is positive and HBV DNA negative, they may be enrolled in the study; if HBsAb is negative and/or HBV DNA is positive, the participant is not eligible for the study.
- For Hepatitis C, all participants will undergo HCVAb during screening. Participants with positive HCVAb tests will be reflex tested for HCV RNA. Only participants with negative HCVAb or HCV RNA will be allowed to enroll.
- For HIV, known history of HIV based on documented history with positive serological test, or positive HIV serologic test at screening, tested at central lab.

20. Baseline standard 12-lead ECG that demonstrates clinically relevant abnormalities that may affect participant safety or interpretation of study results (eg, QTcF >450 ms, complete LBBB, signs of an acute or indeterminate-age myocardial infarction, ST-T interval changes suggestive of myocardial ischemia, second- or third-degree AV block, or serious bradyarrhythmias or tachyarrhythmias).

- If the baseline uncorrected QT interval is >450 ms, this interval should be rate corrected using the Fridericia method only and the resulting QTcF should be used for decision making and reporting.
- If QTcF exceeds 450 ms, or QRS exceeds 120 ms, the ECG should be repeated twice and the average of the 3 QTcF or QRS values used to determine the participant's eligibility.
- Computer-interpreted ECGs should be overread by a physician experienced in reading ECGs before excluding a participant.

Other Exclusion Criteria:

21. Investigator site staff directly involved in the conduct of the study and their family members, site staff otherwise supervised by the investigator, and sponsor and sponsor delegate employees directly involved in the conduct of the study and their family members.

5.3. Lifestyle Considerations

The following guidelines are provided:

5.3.1. Contraception

The investigator or their designee, in consultation with the participant, will confirm that the participant is utilizing an appropriate method of contraception for the individual participant and their partner(s) from the permitted list of contraception methods (see [Appendix 4, Section 10.4.4](#)) and will confirm that the participant has been instructed in its consistent and correct use. At time points indicated in the [SoA](#), the investigator or designee will inform the participant of the need to use highly effective contraception consistently and correctly and document the conversation and the participant's affirmation in the participant's chart. Participants need to affirm their consistent and correct use of the selected methods of contraception, considering that their risk for pregnancy may have changed since the last visit.

In addition, the investigator or designee will instruct the participant to call immediately if the selected contraception method is discontinued and document the requirement to use an alternate protocol-specified method, including if the participant will no longer use abstinence as the selected contraception method, or if pregnancy is known or suspected in the participant or partner.

5.3.2. Meals and Dietary Restrictions

Following a GFD for at least 12 months is required for study entry (see [Section 5.1](#)).

Participants are required to continue to follow a GFD during the study; incidental gluten exposure will be collected daily as part of an eDiary and reviewed at every study visit (see [Section 8.3.1](#)).

Participant's use of herbal medicines and probiotics should be reported on the CRF and should remain stable during the study.

5.3.3. Caffeine, Alcohol, and Tobacco

Participants should avoid excessive consumption of alcohol prior to visits with safety lab assessments as specified in the [SoA](#).

5.3.4. Activity

Participants should avoid strenuous physical activities prior to visits with safety lab assessments as specified in the [SoA](#).

5.4. Screen Failures

Screen failures are defined as participants who consent to participate in the clinical study but are not subsequently randomized in the study. For participants who are screen failed (prior to the run-in GC, Part B only), a minimal set of screen failure information, including demography, screen failure details, eligibility criteria, and any AE or SAE, are required to be collected on the CRF. Screen failure data for participants who are failed (after the run-in GC,

Part B only) will be reported on the CRF. CRF reported data will include, but is not limited to, demographics, medical/CeD history, and prior CeD treatments. Participants who screen-fail (after the run-in GC, Part B only) will also have non-CRF-reported data collected, including, but, not limited to, HLA, CeD serology, biopsy results, CDSB v2.1 data collected up to date of screen failure, and GC IL-2 biomarker data. Non-CRF reported data will be transferred to the sponsor, or sponsor's designee (Pfizer).

Individuals who do not meet the criteria (prior to run-in GC, Part B only) for participation in this study (screen failure) may be rescreened.

Individuals in Part A and Part C who do not meet the criteria for participation in this study (screen failure) may be rescreened *EXCEPT* as noted below.

Repeating HLA genotyping is not needed during rescreening period. Repeating celiac serology and/or EGD with biopsy (for participants in the biopsy substudy) is not required during rescreening if it is within 3 months of the initial assessments during the first screening period.

Participants **cannot be rescreened** if they fail screening due to:

- HLA genotyping assessment at screening.
- Positive for HIV, HBV, or HCV.

For Part B only:

- Individuals who complete the run-in GC, are symptomatic, but are not randomized are eligible for re-screening after 12 months have elapsed.
- Participants **cannot be rescreened** if they fail screening due to:
 - Reasons listed above.
 - Asymptomatic response to the run-in gluten challenge ([Section 8.2.1.1](#)).

6. STUDY INTERVENTION(S) AND CONCOMITANT THERAPY

Study interventions are all prespecified investigational and noninvestigational medicinal products/auxiliary medicinal products, medical devices, and other interventions (eg, surgical and behavioral) intended to be administered to the study participants during the study conduct.

For the purposes of this protocol, study intervention refers to KAN-101 or PBO for KAN-101.

6.1. Study Intervention(s) Administered

Study Intervention(s)		
Intervention Name	KAN-101	PBO
Arm Name (group of participants receiving a specific treatment or no treatment)	Part A: Cohort 1 and 2 Part B: Group 2, 3, and 4 Part C: Group 2, 3, and 4	Part A: N/A Part B: Group 1 Part C: Group 1
Type	Drug	PBO
Dose Formulation	Solution in a single-use glass vial for dilution into saline bag for IV infusion	Solution for infusion in a saline bag
Unit Dose Strength(s)	CCI [REDACTED]	N/A
Dosage Level(s)	CCI [REDACTED]	PBO
Route of Administration	IV	IV
Use	Experimental	Placebo
IMP or NIMP/AxMP	IMP	Placebo
Sourcing	Provided centrally by the sponsor. Further details are presented in the IPM.	Provided locally by the site. Further details are presented in the IPM.
Packaging and Labeling	Study intervention will be provided in glass vials. Each vial will be labeled as required per country requirement. In Part B and Part C, study intervention will be blinded once diluted in a saline bag.	Study intervention will be provided in saline bags. Each saline bag will be labeled as required per country requirement. In Part B and Part C, study intervention will be blinded.

090177e19fcc12ed\Approved\Approved On: 30-Jan-2024 19:45 (GMT)

Study Arm(s)				
Part A (open-label)				
Arm Title	Cohort 1		Cohort 2	
Arm Type	Experimental		Experimental	
Arm Description	Participants will receive 1.2 mg/kg IV every 3 days starting on Day 1 and ending on Day 7.		Participants will receive 3.0 mg/kg IV every 3 days starting on Day 1 and ending on Day 7.	
Associated Intervention Labels	KAN-101		KAN-101	
Part B and Part C (double-blind)				
Arm Title	Group 1	Group 2	Group 3	Group 4
Arm Type	Placebo	Experimental	Experimental	Experimental
Arm Description	Participants will receive PBO IV every 3 days starting on Day 1 and ending on Day 7.	Participants will receive 0.6 mg/kg IV every 3 days starting on Day 1 and ending on Day 7.	Participants will receive 1.2 mg/kg IV every 3 days starting on Day 1 and ending on Day 7.	Participants will receive 3.0 mg/kg IV every 3 days starting on Day 1 and ending on Day 7.
Associated Intervention Labels	PBO	KAN-101	KAN-101	KAN-101

6.1.1. Administration

Administration of KAN-101 will be by IV infusion over approximately 30 minutes for the following dosages: 0.6 mg/kg, 1.2 mg/kg, or 3.0 mg/kg mixed with saline to have the final 250 mL IV infusion solution.

PBO will be 250 mL normal saline only. Administration of PBO will be by IV infusion over approximately 30 minutes.

In Part B and Part C only, for participants who may have experienced adverse events following previous study intervention administration, prophylactic medication such as ondansetron may be administered 30 minutes before subsequent study intervention administration at the discretion of the investigator.

6.2. Preparation, Handling, Storage, and Accountability

1. The investigator or designee must confirm that appropriate conditions (eg, temperature) have been maintained during transit for all study interventions received and any discrepancies are reported and resolved before use of the study intervention.
2. Only participants enrolled in the study may receive study intervention and only authorized site staff may supply, prepare, and/or administer study intervention.

3. All study interventions must be stored in a secure, environmentally controlled, and monitored (manual or automated recording) area in accordance with the labeled storage conditions with access limited to the investigator and authorized site staff. At a minimum, daily minimum and maximum temperatures for all site storage locations must be documented and available upon request. Data for nonworking days must indicate the minimum and maximum temperatures since previously documented upon return to business.
4. Any excursions from the study intervention label storage conditions should be reported to Pfizer upon discovery along with actions taken. The site should actively pursue options for returning the study intervention to labeled storage conditions, as soon as possible. Once an excursion is identified, the study intervention must be quarantined and not used until Pfizer provides permission to use the study intervention. Specific details regarding the excursion definition and information to report for each excursion will be provided to the site in the IPM or other specified location.
5. Any storage conditions stated in the SRSD will be superseded by the storage conditions stated on the label. See the IPM for storage conditions of the study intervention once diluted.
6. Study interventions should be stored in their original containers.
7. The investigator, institution, head of the medical institution (where applicable), or authorized site staff is responsible for study intervention accountability, reconciliation, and record maintenance (ie, receipt, reconciliation, and final disposition records), such as the IPAL or sponsor-approved equivalent. All study interventions will be accounted for using a study intervention accountability form/record.
8. Further guidance and information for the final disposition of unused study interventions are provided in the IPM. All destruction must be adequately documented. If destruction is authorized to take place at the investigator site, the investigator must ensure that the materials are destroyed in compliance with applicable environmental regulations, institutional policy, and any special instructions provided by Pfizer.

Upon identification of a product complaint, notify Pfizer within 1 business day of discovery as described in the IPM.

6.2.1. Preparation and Dispensing

See the IPM for instructions on how to prepare the study intervention for administration. Study intervention should be prepared and dispensed by an appropriately qualified and experienced member of the study staff (eg, physician, nurse, physician's assistant, nurse practitioner, pharmacy assistant/technician, or pharmacist) as allowed by local, state, and institutional guidance. A second staff member will verify the dispensing.

6.3. Assignment to Study Intervention

Allocation of participants to treatment groups will proceed through the use of an IRT system. The site personnel (ex. study coordinator or specified designee) will be required to enter or select information including but not limited to the user's ID and password, the protocol number, and the participant number. The site personnel will then be provided with a randomization number corresponding to the assigned treatment group, and DU or container number(s) when study intervention is being supplied via the IRT system. The IRT system will provide a confirmation report containing the participant number, randomization number, and DU or container number assigned. The confirmation report must be stored in the site's files.

Part A is an open-label study. The investigator's knowledge of the treatment assignment must not influence the decision to enroll a particular participant or affect the order in which participants are enrolled. Potential bias will be reduced by the following steps: central randomization and DSMB review.

Study intervention will be dispensed at the study visits summarized in the [SoA](#).

The study-specific IRT reference manual and IPM will provide the contact information and further details on the use of the IRT system.

6.4. Blinding

This is a 3 part study; Part A is open-label and Part B and Part C are double-blinded .

6.4.1. Blinding of Participants

- **Part A** is open-label.
- **In Part B and Part C**, participants and their caregivers will be blinded to their assigned study intervention.

6.4.2. Blinding of Site Personnel

- **Part A** is open-label.
- **In Part B and Part C**, investigators and other site staff will be blinded to participants' assigned study intervention. Participants will be assigned to receive study intervention according to the assigned treatment group from the randomization scheme. Investigators will remain blinded to each participant's assigned study intervention throughout the course of the study.

Unblinded personnel include site staff involved in study intervention preparation and allocation (eg, data systems support and pharmacists).

6.4.3. Blinding of the Sponsor

- **Part A** is open-label. The data for dose escalation in Part A will be presented and reviewed by the DSMB in an open-label, unblinded manner.

- **For Part B and Part C**, sponsor staff will be blinded to participants' assigned study intervention, except for sponsor staff involved in the assignment or distribution of study intervention. Sponsor staff who are not directly involved with the conduct of this study will prepare analyses and documentation containing unblinded data while the study is ongoing to support interactions with the DSMB.

6.4.4. Breaking the Blind

The IRT will be programmed with blind-breaking instructions. In case of an emergency, the investigator has the sole responsibility for determining if unblinding of a participant's treatment assignment is warranted. Participant safety must always be the first consideration in making such a determination. If the investigator decides that unblinding is warranted, the investigator should make every effort to contact the study medical monitor prior to unblinding a participant's treatment assignment unless this could delay further management of the participant. If a participant's treatment assignment is unblinded, Pfizer must be notified within 24 hours after breaking the blind. The date and reason that the blind was broken must be recorded in the source documentation and CRF.

The study--specific IRT reference manual and IPM will provide the contact information and further details on the use of the IRT system.

6.5. Study Intervention Compliance

The existing clinical site's documentation system should capture all pertinent/required information on the preparation and administration of the dose.

Compliance with the study intervention is defined as receiving 100% of the doses as specified per protocol.

6.6. Dose Modification

In Part B and Part C, no dose modification is allowed following selection of doses based on safety and tolerability of doses studied in Part A.

In Part A, the decision to proceed to the next dose level of KAN-101 (either an increase or a decrease) will be made by the study team and DSMB during the dose escalation safety period (see [Section 6.6.1](#)).

Details of the DSMB are presented in [Section 10.1.5](#).

If the decision is made to dose escalate, it is the sponsor's discretion whether to proceed with escalation, expand the same dose cohort, or to modify doses based on emerging data.

6.6.1. Dose Escalation Safety Review Period for Part A

In Part A, the dose escalation safety review period is from the beginning of IV administration through Day 15 prior to GC. Any AEs that meet DLT criteria ([Section 4.1.1.1.1](#)) but occur after the dose escalation safety monitoring period of Part A may be considered by the DSMB/Sponsor in the evaluation of Part A dose escalation and Part B dose selection.

The length of monitoring periods for safety review is supported by nonclinical exposure data and FIH clinical data, suggesting KAN-101 will have cleared 5 half-lives, and clinical data demonstrating that the tolerance induction mechanism can develop within 1 week of dosing. Participants will be monitored in the clinic for 4 hours following the IV administration of study intervention.

AEs and any abnormal clinical parameters, including laboratory findings and available PK data, observed during this period will be used by the DSMB to determine whether dose escalation should proceed. DSMB review of ongoing safety data will continue after dose escalation has either been completed or stopped and participants remain active in the study.

Dose escalation in Part A can proceed after the following criteria are met:

- All 3 participants have been dosed.
 - DSMB, sponsor medical monitor and investigators who enrolled participants have reviewed all available safety data for dosed subjects, including:
 - A minimum of 1 week safety and tolerability data after the last study intervention dose;
- AND**
- All available PK data after the last study intervention dose.

6.6.1.1. Individual and Cohort Stopping Rules

Dose escalation stopping rules will be used to determine whether the MTD has been attained. Dose escalation will be stopped if it is determined that the limits of safety and/or tolerability have been reached based on the criteria described in this section. This decision will be made after a discussion takes place between the DSMB, the sponsor study team and the investigator. The sponsor study team may not overrule the DSMB or investigator's decision to stop dose escalation. If dose escalation is stopped because of any of these criteria, additional cohorts may receive the same or lower doses of the study intervention. If any dose cohort is repeated, this additional cohort will be considered a separate cohort for the purpose of these dose escalation stopping rules.

For DLT definition for Part A and further details, see [Section 4.1.1.1.1](#).

At any time:

- Any TEAE at Grade 3 or higher experienced during the study will be reviewed by DSMB.

- Any \geq Grade 4 AE will result in notification of the FDA in parallel with DSMB and study dosing and enrollment will be paused pending review by FDA.
 - The study would only continue after consultation with the FDA.
- No participant with a DLT will be replaced.

In Part A:

- If a participant experiences a DLT, no additional doses will be administered to that participant.
- If 1 of the first 3 participants experiences a DLT in a given cohort, 3 additional participants will be enrolled and evaluated in that cohort before dose escalation can occur if recommended by the DSMB and only after consultation with the FDA for any \geq Grade 4 AE.
- If 2 or more participants experience a DLT at a given dose during the dose escalation period of Part A, then that dose level will be considered a NTD and no further escalation will proceed.

In Part B and Part C:

- DSMB will review unblinded available clinical, laboratory and PK data (if available) periodically or if there is a Grade 3 or above, related AE during treatment period and will make recommendations for study continuation as defined in the DSMB charter.

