4.1.1. Part A: Phase 1b, Open-Label, Multiple Ascending Dose Study

Part A is a Phase 1b, open-label, MAD study design to assess the safety, tolerability and PK of KAN-101 in adult participants (18 to 70 years inclusive) with histology-confirmed CeD. Up to 18 participants who meet study inclusion/exclusion criteria may be randomized in the study.

Part A comprises 3 periods:

- **Screening period:** Up to 28 days before the first dose
- **Treatment period:** 7 days
 - Eligible participants will be administered IV study intervention on Day 1, Day 4, and Day 7 (see [Section 6.1.1](#)).
 - Post infusion, participants will be monitored in the clinic for 4 hours for infusion-related reactions (see [Appendix 9](#)).
 - The dose cohorts planned for Part A are:
 - 1.2 mg/kg (Cohort 1)
 - 3.0 mg/kg (Cohort 2)
 - Based on emerging data from previous and ongoing cohorts, doses planned may be repeated, modified and other doses may be explored in additional cohorts. If the exposures in the subsequent dose are projected to exceed the exposure limits pre-specified, that dose will not be explored.
- **Observation/Follow-up period:** 21 days
 - **Post-dosing GC on Day 15:** All participants administered KAN-101 will return to the clinic on Day 15 to receive a 1-day 9g oral GC to assess exploratory endpoints (plasma IL-2 biomarker response to gluten and collect symptom information).
 - **Safety follow-up visit on Day 28:** includes assessment of AEs, clinical signs and symptoms, and review of clinical laboratory values.

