4.1.1.1.1. Dose-Limiting Toxicities (Part A Only)

- Dose-limiting toxicity will be defined as any Grade 2 AE lasting longer than 14 days or any \geq Grade 3 AE assessed as related to study intervention.
- If a DLT is observed in Part A, the study will be paused and the DSMB will review the information prior to dosing additional participants. The cohort will be expanded to 6 participants total before dose escalation is reviewed.
- The NTD is the dose level at which 2 or more participants experience a DLT during the dose escalation safety review period. The MTD will be defined as the dose level immediately below the NTD.
 - Of note, dose escalation may not identify an NTD or MTD.
 - If an MTD is identified in Part A, dose levels in Part B will not exceed the MTD.

DLTs DO NOT include:

- AEs attributable solely to intercurrent illness or other concomitant medications.

Stopping rules in case of DLT are presented in [Section 6.6.1.1](#).

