10.9. Appendix 9: Infusion-Related Reactions

Participants will be monitored in the clinic for 4 hours following IV study drug administration for IRR. IRR may include, but are not limited to: erythema, induration, ecchymosis, pain, and pruritus.

If an IRR occurs during study intervention administration, the following treatment recommendations are provided and may be modified per local treatment standards and guidelines as appropriate:

- **Grade 1 (mild):** Infusion rate modification not indicated. Administer symptomatic treatment (eg, antihistamines, antipyretics, antiemetics) as needed. Closely monitor participant until resolution. Prophylaxis with diphenhydramine 50 mg (or equivalent) and/or acetaminophen/paracetamol 325 to 1000 mg is recommended at least 30 min prior to future study intervention infusions.
- **Grade 2 (moderate):** Slow infusion rate to $\leq 50\%$ of the original infusion rate and treat symptoms with appropriate medical therapy, including but not limited to antihistamines, antipyretics, and analgesics. Increase monitoring of vital signs as medically indicated until participant is deemed stable. Prophylaxis with diphenhydramine 50 mg (or equivalent) and/or acetaminophen/paracetamol 325 to 1000 mg is recommended at least 30 min prior to future study intervention infusions.
- **Grade 3 (severe):** Stop infusion and institute appropriate symptom-directed therapy, including but not limited to antihistamines, antipyretics, corticosteroids, bronchodilators, and O₂. Increase monitoring of vital signs as medically indicated until participant is deemed stable.
 - If the reaction has not resolved within 6 hours, the remainder of the infusion will not be administered and study intervention will be permanently discontinued.
 - Following the completion or termination of a restarted infusion due to an IRR:
 - All participants must be monitored until resolution of symptoms or for 2 hours in the absence of additional symptoms.
 - Prophylaxis with diphenhydramine 50 mg (or equivalent) and/or acetaminophen/paracetamol 325 to 1000 mg is recommended at least 30 min prior to future study intervention infusions.
 - The next infusion should initiate at a rate of 2 hours per dose, or 50% of the rate at which the reaction occurred. If no IRRs are observed within the first 30 minutes, the infusion rate may increase to 30-minutes-per dose rate as outlined in [Section 6.1.1](#).

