- If second occurrence of Grade 3 or greater IRR, permanently discontinue study intervention.

- **Grade 4 (life-threatening):** Stop infusion and immediately institute appropriate symptom directed therapy and supportive measures as necessary, including but not limited to, corticosteroids, bronchodilators, O₂/respiratory support, and vasopressors. Hospitalization and/or intensive care unit admission may be indicated.
- Permanently discontinue study intervention.

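### In Part A, the DLT stopping rule and the infusion-reaction guidance in Appendix 9 differ on whether dosing continues after a first related Grade 3 reaction that resolves within 6 hours, and neither says which governs

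*Protocol*

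**What the plan says.** Three parts of the Protocol bear on this.

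- **DLT definition (Section 4.1.1.1.1, Part A only).** A DLT includes an event at or above this threshold: "Grade 3 AE assessed as related to study intervention". The one listed exclusion is "AEs attributable solely to intercurrent illness or other concomitant medications". Infusion reactions are not mentioned.
- **Stopping rule (Section 6.6.1.1, Part A).** "If a participant experiences a DLT, no additional doses will be administered to that participant". No exception is given. The same section says that participants with a DLT are not replaced.
- **Infusion-reaction guidance (Appendix 9).** For a Grade 3 reaction the infusion is stopped and symptoms are treated. Treatment ends for good if the reaction is unresolved at 6 hours. The text then refers to a restarted infusion, recommends premedication before later infusions, and adds: "The next infusion should initiate at a rate of 2 hours per dose, or 50% of the rate at which the reaction occurred". It closes the Grade 3 branch with: "If second occurrence of Grade 3 or greater IRR, permanently discontinue study intervention".

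Appendix 9 is not restricted to Parts B and C. The Part A description in Section 4.1.1 points to it: "Post infusion, participants will be monitored in the clinic for 4 hours for infusion-related reactions". Section 7.1.4 refers to it for infusion interruptions, and the risk table in Section 2.3.1 for future infusions; neither limits it by part.

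**The concern.** A Part A investigator faced with a related Grade 3 infusion reaction finds one text that ends dosing and another that explains how to give the next dose. Doses are 3 days apart, so the choice has to be made quickly. The first issue is re-exposure after an event that the protocol itself classes as dose-limiting. The second is what the cohort data mean: one rule leaves the participant with one or two infusions, the other with up to three, the later ones premedicated and started more slowly. In cohorts of 3 to 6, a single participant handled differently is a visible share of the PK and exposure summaries.

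**Working it through.** The plan gives no figure to reproduce, so the check is a comparison of the texts followed by a count of doses.

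**Is a Grade 3 infusion reaction a DLT?** It is if the investigator judges it related. The definition has no exemption for infusion reactions. The timing also fits, because Section 6.6.1 says "the dose escalation safety review period is from the beginning of IV administration through Day 15 prior to GC", which covers all three infusions. A reaction judged unrelated is not a DLT, and no conflict arises.

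**Doses still planned.** There are 3 infusions, on Days 1, 4 and 7. After a Day 1 reaction 3 − 1 = 2 remain, after a Day 4 reaction 3 − 2 = 1, and after a Day 7 reaction 3 − 3 = 0.

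| Part A case (related reaction) | Later infusions under 6.6.1.1 | Later infusions under Appendix 9 | Difference |
|---|---|---|---|
| First Grade 3, Day 1, resolved within 6 h | 0 | up to 2 | up to 2 |
| First Grade 3, Day 4, resolved within 6 h | 0 | up to 1 | up to 1 |
| First Grade 3, Day 7, resolved within 6 h | 0 | 0 planned | none; only the interrupted infusion is open |
| Grade 3, unresolved at 6 h | 0 | 0 | none |
| Grade 4 | 0 | 0 | none |

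The entries are maxima because a second reaction of Grade 3 or above ends dosing under Appendix 9 as well, and dosing may stop for other reasons.

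**The interrupted infusion.** Section 6.6.1.1 bars further doses but does not say whether finishing a stopped infusion counts as one. Appendix 9 assumes that a restart may happen without ordering it. Whether the texts conflict on this step cannot be decided from the documents.

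**What follows for the data.**
- Part A PK is sampled on Days 1 and 7 (Section 1.3.1). With no Day 7 infusion there is no Day 7 profile.
- Section 7.1 withholds the gluten challenge from participants who withdraw from treatment without three full doses. Dosing stopped after Day 1 or Day 4 therefore rules it out. Under Appendix 9 it remains possible if the interrupted dose is completed and the others are given.
- One participant is 1/3 = 33% of a 3-person cohort or 1/6 = 17% of a 6-person cohort. These are shares, not estimates of how often the event occurs.

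**What does not follow.** Section 4.1.1.1.1 sets the non-tolerated dose by the number of participants with a DLT. The participant is counted once the reaction occurs, whether or not dosing continues. Cohort expansion and the escalation decision are therefore the same under either text.

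**The case against.** The best reply is that the texts can be read together. Appendix 9 introduces its content as recommendations that sites may adapt to local treatment standards, while Section 6.6.1.1 is mandatory and specific to Part A. A site that stops dosing arguably breaches nothing in Appendix 9, whose premedication and rate advice can be read as applying only if a later infusion is given. This has force: a reader might infer that no site could comply with both texts, and that goes too far.

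It does not settle the matter. Appendix 9 goes beyond supportive care and sets its own thresholds for ending treatment, which is the subject of Section 6.6.1.1. The adaptation it allows is to local standards; it does not mention the Part A stopping rule. Specificity does not decide it either, since one text is specific to Part A and the other to infusion reactions.

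Two further replies stand in part. The first-in-human study reported no Grade 3 treatment-emergent events among 41 dosed participants (Section 2.2.3), so the event may be rare; its doses, however, went only to 1.5 mg/kg, below the 3.0 mg/kg cohort here. Also, Section 4.2 describes moving to Part B after the 3.0 mg/kg cohort was completed, and the Part A SAP (Section 1) records study termination. The prospective effect is therefore probably small, although Sections 4.1.1 and 4.3.2 still allow repeated or additional Part A cohorts.

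**Conclusion.** The inconsistency is real but narrow. It applies to a Part A participant with a first Grade 3 infusion reaction, judged related and resolved within 6 hours, on Day 1 or Day 4. There the texts differ by up to 2 or up to 1 further infusions, with consequences for Day 7 PK and the Day 15 challenge. The Part A SAP (Section 6.3) no longer reports the exploratory endpoints, so Day 7 PK, a secondary endpoint, is the more durable of the two.

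Some stronger conclusions that a reader might draw are not supported. Appendix 9 presupposes a restart but does not direct one. Not every Grade 3 reaction is affected, because an unresolved one ends treatment under both texts. A Day 7 reaction is affected only if finishing the interrupted infusion counts as a further dose, which is undefined. The DLT count is not distorted. With the planned cohorts complete, the documents do not show a current re-exposure hazard.

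The conclusion assumes that the reaction is assessed as related, and that Appendix 9 applies to Part A as its cross-references indicate. What remains is the rule for any further Part A cohort and the record of how any past Part A Grade 3 reaction was handled.

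**What to change.** Reconcile Sections 4.1.1.1.1 and 6.6.1.1 with Appendix 9. Add a part-specific sentence to the Grade 3 branch of Appendix 9 stating which text governs a Part A infusion reaction that meets the DLT definition. It should cover the interrupted infusion and the later doses separately, and Section 6.6.1.1 should be worded to match. The choice of rule belongs to the sponsor and the DSMB.

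If no further Part A cohort is planned, record in the study report which text was applied to any Part A Grade 3 infusion reaction, with the number of doses that participant received.

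The cost is one or two sentences in an amendment or clarification letter, with no added procedures or participants.
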